11.7.3. ECG

Parameter	Units	Change from Baseline of Potential Clinical Concern	Potential Clinical Concern Value
-----------	-------	--	----------------------------------

Heart Rate	bpm	None	Supine: < 50 or > 120
QRS interval	msec	Increase of > 25% when baseline QRS >100 msec Increase of > 50% when baseline QRS ≤100 msec	>200 msec
QTcF	msec	≥ 60 msec	≥500 msec
PR Interval	msec	Increase of > 25% when baseline PR >200 msec Increase of > 50% when baseline PR ≤200 msec	>300 msec

11.8. Appendix 8: Multicenter Studies

11.8.1. Definition of Geographic Region

Clinical sites will be clustered by geographic region since the number of subjects per clinical site is expected to be rather small. Geographic regions will be defined based on geographic proximity, similarity of medical practice in diabetes, and number of subjects per region. Subjects per region will be constrained such that the region with the largest sample size is no more than 3 times that of the region with the smallest sample size. The clustering will be finalized after clinical site selection and randomization are complete.

- Final classification of geographic region

Region	State	Investigational Site
USA - North	New York, Pennsylvania, Ohio, Indiana, Illinois, Michigan, Missouri, Nebraska, Kansas	PPD
USA – South Atlantic	North Carolina, South Carolina, Georgia, Florida	
USA – South Central	Kentucky, Alabama, Arkansas, Louisiana, Texas	
USA - West	Idaho, Colorado, New Mexico, Arizona, Utah, Nevada, Washington, California	

11.9. Appendix 9: Examination of Covariates, Subgroups & Other Strata

11.9.1. Strata and Covariates

The randomization for this study is stratified by the following baseline characteristics:

- Age at randomization (<65 years versus \geq 65 years)
- Weight at Screening (<90 or \geq 90 kg)
- Background antidiabetic therapy (diet and exercise or stable dose of metformin)

The primary analysis of HbA_{1c} change from baseline will use a mixed-effect model with repeated measures (MMRM), which includes HbA_{1c} change from baseline at all post-baseline visits as dependent variables; treatment, region, age category, weight category, background antidiabetic therapy, visit week, treatment-by-visit interaction as fixed effects; baseline HbA_{1c} as a continuous covariate; and subject as a random effect.

11.9.2. Examination of Subgroups

The primary efficacy endpoint will be analyzed for the following subgroups using a MMRM model described in Section 7.

- Baseline HbA_{1c} (< 8% or \geq 8%)
- Region (USA – North, USA – South Atlantic, USA – South Central, USA - West)
- Age at randomization (<65 or \geq 65 years)
- Weight at Screening (<90 or \geq 90 kg)
- Background antidiabetic therapy (diet and exercise or stable dose of metformin)
- Gender (male or female)
- Race (white or non-white)
- Ethnicity (Hispanic or non-hispanic)
- Duration of diabetes category (<5, 5 to 10 or >10 years)

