6.8. Medical History

Subject data listings and summary tables will be provided for the following current and/or past conditions:

- cardiovascular medical history
- diabetes related medical history
- medical/surgical procedure history
- gastrointestinal (GI) medical history
- cancer history

- pneumonia medical history
- skin medical conditions
- thyroid medical history, thyroid cancer history, benign thyroid medical conditions
- thyroid cancer family history
- pancreatitis family history
- pancreatic cancer family history
- other medical history
- other medical/surgical surgery

The number and percentage of subjects with current and/or past medical histories listed above will be reported by treatment group. A summary of duration of diabetes disease history in years will be provided. The duration of diabetes disease history is calculated as the years lapsed between screening visit date and T2DM diagnosis date.

In addition, by subject listings of medical and family history status and all the medical conditions listed above will be provided.

All summaries will be performed using the safety population.

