11.6.2. Missing Date Imputation

In general, partial dates will be imputed as follows:

A partial event start date, partial start dates of prior and concomitant medications or partial diagnosis date will be assumed to be the earliest possible date consistent with the partial date.

- If year is missing, the year will be assumed to be the year part of informed consent date of that subject;
- If month is missing, the month will be assumed to be January;
- If day is missing, it will be assumed to be the first day of the month.
- In the case of a completely missing start date, the start date will be assumed to be prior to date of the first administration of study drug.

Partial event or medication stop dates will be assumed to be the latest possible date consistent with the partial date.

- If month is missing, it will be assumed to be December;
- If day is missing, it will be assumed to be the last day of the month.
- In the case of completely missing stop date, the stop date will be assumed to be after the date of the last study visit; the event or medication are considered as ongoing.

For AE date imputation this rule will be followed but will be more conservative in nature consistent with the therapy phase (see [Appendix 4: Treatment Periods](#) for details).

Since only the year of birth is recorded for subjects in this study, the age of the subjects for analysis purposes is calculated using June 30 of the birth year as the imputed subject birth date.

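### The SAP's rule for partial diabetes diagnosis dates overstates duration when the month is missing and reduces it to under one year when the year is missing

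*SAP*

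**What the plan says.** SAP 6.8 defines the variable: "The duration of diabetes disease history is calculated as the years lapsed between screening visit date and T2DM diagnosis date". It is summarised in Table 1.24. SAP 7.1.1.3 and 11.9.2 use it as one of nine subgroups for the primary endpoint, "Duration of diabetes category (<5, 5 to 10 or >10 years", reported in Table 2.17.

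SAP 11.6.2 gives the date rules. Diagnosis dates share a sentence with event and medication start dates: a "partial diagnosis date will be assumed to be the earliest possible date consistent with the partial date". The bullets beneath it then treat each missing part in turn. The bullet on the year reads "If year is missing, the year will be assumed to be the year part of informed consent date of that subject". The next one, on the month, reads "If month is missing, the month will be assumed to be January". The one on the day reads "If day is missing, it will be assumed to be the first day of the month". A last bullet places a completely missing start date before first dosing but assigns no calendar date. Adverse event dates get their own variant through Appendix 4. Diagnosis dates get no exception.

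The same section says that only birth year is recorded and that "the age of the subjects for analysis purposes is calculated using June 30 of the birth year as the imputed subject birth date". SAP 11.9.1 lists the randomization stratum as "Age at randomization (<65 years versus" 65 years or more.

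Protocol 5.1, inclusion criterion 2, requires a diagnosis of type 2 diabetes at least 3 months old.

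**The concern.** An earliest-date convention can suit events and medications, where it decides whether something began before or during treatment. Here the imputed date feeds a continuous baseline variable and a subgroup with fixed cut-points, so moving the date back always lengthens the duration.

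The missing-year bullet goes the other way. For a diagnosis that must precede screening, the consent year is the latest plausible year, so the bullet contradicts the sentence that introduces it. A subject with long-standing diabetes would be analysed with the recently diagnosed.

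At stake are the accuracy of Table 1.24 and group membership in Table 2.17. Moving subjects between categories mixes them and blurs any real difference in treatment effect by duration.

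**Working it through.** The documents give no count of incomplete or misclassified dates, so there is no figure of the plan's to reproduce on this point. The sample size has no diagnosis date among its inputs: 133 per arm with margin 0.4, SD 1 and one-sided 0.025 gives power 0.9015 (noncentral t), matching the stated 90%.

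**Inputs from the SAP:** the duration definition (6.8), the cut-points (11.9.2) and the imputation rules (11.6.2). I take years as days divided by 365.25.

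**1. Month missing.** The error is the true diagnosis date minus 1 January of the same year. It lies between 0 and 1 year, averages about 0.5 if diagnoses are spread evenly over the year, and is never negative.

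*Example with assumed dates:* screening 15 Feb 2016, true diagnosis 15 Nov 2011.
- True duration: 1,553 / 365.25 = 4.25 years, under 5.
- Year only, 1 Jan 2011: 1,871 / 365.25 = 5.12 years, in 5 to 10.
- Year only, 30 June 2011: 1,691 / 365.25 = 4.63 years, still under 5.

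*Share moved among year-only dates.* Simulation with assumed gamma durations, mean 6 to 8 and SD 5 to 6 years, screening date uniform within the year:

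| Rule | Mean bias | Moved up | Moved down |
|---|---|---|---|
| 1 January | +0.50 y | about 6% to 7% (5.7% to 7.9% over all mean/SD combinations tried) | none |
| Mid-year | 0.00 y | about half of 3% (total 2.7% to 3.8% over all combinations) | about the other half |

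*Subjects out of 300.* Let f be the share of dates with no month and d the share of subjects per year of duration around each cut-point (both assumed). The January rule moves 300 × f × 2 × d × 0.5.
- f = 5%, d = 3%: 0.45
- f = 25%, d = 6%: 4.5
- f = 50%, d = 9%: 13.5

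With mid-year the mean absolute error is 0.25 year instead of 0.5, so each count halves: 2.25 in the middle case.

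**2. Day only missing.** The error is at most about 30 days. With f = 50% and d = 6%: 300 × 0.5 × 2 × 0.06 × 15 / 365.25 = 0.7 subject.

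**3. Year missing.** Take screening and consent in the same calendar year.
- Month also missing: the date becomes 1 January of that year, so duration is under 1 year whatever the truth. In the example, 1 Jan 2016 to 15 Feb 2016 is 45 / 365.25 = 0.12 year, below the 0.25 year that entry requires.
- Month known, say November: 1 Nov 2016 falls after screening, giving −260 / 365.25 = −0.71 year. No cap is stated.

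Every such subject is placed in the under-5 category. Under the same assumed distributions, 48% to 63% of subjects would truly have 5 years or more.

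**The case against.** **The affected set may be small.** Complete dates are untouched, and the eCRF page that collects diabetes history is not available. In the middle case above, mid-year leaves about 2 fewer subjects of 300 misplaced. This stands, and it sets the size of the point. It does not make the January rule unbiased.

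**A date without a year may fall under the completely-missing bullet**, in which case no duration is computed. That bullet speaks of start dates and does not name diagnosis dates, while the consent-year bullet sits directly under a sentence that does. If the lenient reading is intended, the text should say so.

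**Birth and diagnosis dates are different variables with separate rules.** Agreed: the 30 June birthday does not contradict the January rule. It only shows that the SAP already accepts mid-year imputation. The contradiction is between the consent-year bullet and the earliest-date sentence.

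**A stronger reading a reader might infer:** that the age category is rebuilt from the 30 June birthday instead of the randomized stratum, so the under/over-65 analyses use wrong groups. The documents do not say this. They leave the source of AGEGR1 open. The phrase about age for analysis purposes leans towards derived age. The titles of Table 2.10 (age category at randomization) and Listing 133 (stratifying factors used in the models) fit the stratum. If age were derived and the IVRS held true birthdays (both assumptions), about 25% of subjects turning 65 in the randomization year would change group. At an assumed 1% to 4% of subjects, that is 300 × 0.01 × 0.25 = 0.75 to 300 × 0.04 × 0.25 = 3 subjects, split about evenly in direction.

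**Conclusion.** The point holds for diabetes duration and is minor. The one-sided error for missing months and the contradiction for missing years follow from the SAP text alone, and the missing-year rule is the clearer fault. The percentages rest on the assumed gamma distributions and apply only to subjects with year-only dates; the counts also rest on an assumed frequency of incomplete dates.

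The documents do not support saying that subjects near the cut-points are generally misclassified, or that the trial's conclusion is at risk. The rules are the same in both arms, duration is not a term in the primary MMRM, and the non-inferiority test, alpha and sample size are unchanged. The source of the age category is a matter for clarification. No defect is shown for weight category or background therapy.

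**What to change.** In SAP 11.6.2, take the type 2 diabetes diagnosis date out of the earliest-date rule and state instead:

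- month missing: impute 30 June of the recorded year; day missing: impute mid-month;
- the imputed date is no later than 3 months before screening, in line with inclusion criterion 2;
- year missing: leave duration missing;
- report with Tables 1.24 and 2.17 the number of subjects with an imputed or missing diagnosis date, by arm.

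As a secondary clarification, state in SAP 11.9.1 and 11.9.2 that the age category in the MMRM and the age subgroup are the stratum used at randomization.

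The cost is a few sentences and a small programming change. A few subjects may have no duration category and would drop out of the Table 2.17 model, so the SAP should say so.

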11.10. Appendix 10: Multiple Comparisons & Multiplicity

11.10.1. Handling of Multiple Comparisons & Multiplicity

Not applicable.

11.11. Appendix 11: Model Checking and Diagnostics for Statistical Analyses

11.11.1. Model Checking and Diagnostics for Statistical Analyses

1. Example SAS code for the primary efficacy analysis with imputation

Step 1a: Transpose the data horizontally and then impute data assuming missing at random (EFFIM)

```
PROC MI DATA= EFF OUT= EFFIM NIMPUTE=100 SEED=4408572;
  BY TRT01PN;
  MCMC CHAIN=multiple;
  VAR BASE CHG_W1 CHG_W4 CHG_W8 CHG_W12 CHG_W16 CHG_W20 CHG_W26;
  RUN;
```

Note: need to remove all imputed values before Week 26 and retain imputed values at Week 26 only.

Step 1b: Add 0.4 to the imputed value at Week 26 in the liquid product arm and transpose data in vertical structure (EFFIM2)

Step 2: Exclude HbA1c change from baseline at Week 1 and perform MMRM for each imputed dataset

```
Ods output SLICES=SLICE LSM SLICEDIFFS=SLICEDIFF;
```

```
PROC MIXED DATA= EFFIM ;
  BY _imputation_;
  CLASS USUBJID REGION WGTGR1 AGEGR1 PRIORDTX TRT01PN AVISITN;
  MODEL CHG= BASE REGION WGTGR1 AGEGR1 PRIORDTX TRT01PN AVISITN
  TRT01PN*AVISITN BASE*AVISITN/ DDFM=KR;
  REPEATED AVISITN/SUB=USUBJID TYPE=UN;
  SLICE TRT01PN*AVISITN/sliceby(AVISITN='26') means pdiff cl cov;
  RUN;
```

Step 3: Combine results using PROC MIANALYZE

```
PROC SORT DATA=SLICE LSM; BY TRT01PN IMPUTATION; RUN;
PROC MIANALYZE DATA=SLICE LSM EDF=CDF*;
BY TRT01PN;
MODELEFFECTS ESTIMATE;
STDERR STDERR;
RUN;
```

```
PROC MIANALYZE DATA=SLICEDIFF;
MODELEFFECTS ESTIMATE;
STDERR STDERR;
RUN;
```

*CDF=complete-data degrees of freedom. This is used to calculate the adjusted degrees of freedom for the combined results.

2. Example SAS code for the by-subgroup analysis of the primary endpoint with imputation

Follow the same steps as for the example SAS code for the primary analysis except in the step 2 additional interaction terms need to be added.

Subgroup variable: Baseline HbA1c <8% or >=8%

```
ods output SLICES=SLICELSM1 SLICEDIFFS=SLICEDIFF1;
PROC MIXED DATA= EFFIM;
  BY imputation;
  CLASS USUBJID REGION WGTGR1 AGEGR1 PRIORDTX TRT01PN AVISITN HBGR1;
  MODEL CHG= HBGR1 REGION WGTGR1 AGEGR1 PRIORDTX TRT01PN AVISITN
TRT01PN*AVISITN HBGR1*TRT01PN HBGR1*AVISITN
          HBGR1*TRT01PN*AVISITN/ DDFM=KR;
  REPEATED AVISITN/SUB=USUBJID TYPE=UN;
  SLICE HBGR1*TRT01PN*AVISITN/sliceby(AVISITN='26') means pdiff cl
cov;
RUN;
```

Subgroup variable: Baseline Weight <90 or >=90 kg

```
ods output SLICES=SLICELSM2 SLICEDIFFS=SLICEDIFF2;
PROC MIXED DATA= EFFIM;
  BY imputation;
  CLASS USUBJID REGION WGTGR1 AGEGR1 PRIORDTX TRT01PN AVISITN;
  MODEL CHG= BASE REGION WGTGR1 AGEGR1 PRIORDTX TRT01PN AVISITN
TRT01PN*AVISITN BASE*AVISITN WGTGR1*TRT01PN WGTGR1*AVISITN
          WGTGR1*TRT01PN*AVISITN/ DDFM=KR;
  REPEATED AVISITN/SUB=USUBJID TYPE=UN;
  SLICE WGTGR1*TRT01PN*AVISITN/sliceby(AVISITN='26') means pdiff cl
cov;
RUN;
```

3. Example SAS code for the secondary efficacy analyses using MMRM without imputation

```
PROC MIXED DATA= INDATA ;
  CLASS USUBJID REGION WGTGR1 AGEGR1 PRIORDTX TRT01PN AVISITN;
  MODEL CHG= BASE REGION WGTGR1 AGEGR1 PRIORDTX TRT01PN AVISITN
TRT01PN*AVISITN BASE*AVISITN/ DDFM=KR;
  REPEATED AVISITN/SUB=USUBJID TYPE=UN;
  SLICE TRT01PN*AVISITN/slice=AVISITN means pdiff cl cov;
RUN;
```

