9.4. Key Elements of Analysis Plan

9.4.1. Primary Analyses

The primary endpoint is the change from baseline in HbA1c at Week 26. The primary analysis will include all HbA1c values collected at scheduled visits up to Week 26. This will include values after hyperglycemia rescue and discontinuation from investigational product. The primary analysis of the primary endpoint will be conducted using a mixed-effect model with repeated measures (MMRM) in the ITT Population. MMRM will use all available data. Imputation under the non-inferiority null hypothesis for missing data will be incorporated [Koch, 2008]. Multiple imputation will be used to replace missing data of change from baseline of HbA1c at Week 26 for all patients in both treatment arms as a first step, and then to make all the imputed values for the liquid drug product arm worse by the non-inferiority margin 0.4.

Multiple imputation approach uses separate covariance parameter estimation for each arm, and also separate regression parameters are estimated on baseline covariates within each arm. For subjects with missing data the imputation will use means and variances-covariances from subjects in that treatment group where that subject with missing data belongs. This approach will be used for all data missing post withdrawal due to lost to follow-up or withdraws consent.

Non-inferiority testing will be performed at a one-sided alpha of 0.025 and non-inferiority margin of 0.4.

Further details of the imputation method for the primary analysis will be provided in the RAP.

The primary MMRM model will include HbA1c change from baseline at all post-baseline visits as dependent variables; treatment, region, age category, weight, background antidiabetic therapy, visit week, and treatment-by-week interaction as fixed effects; baseline HbA1c as a continuous covariate; and subject as a random effect. Treatment effects estimates (and associated CI) of albiglutide liquid drug product will be evaluated within this MMRM model as least squares means contrasts relative to the lyophilized drug product. An unstructured covariance matrix will be used for the MMRM analysis, unless the model does not converge, in which case the covariance matrix will be decided upon model convergence status and the Akaike information criterion.

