2. SUMMARY OF KEY PROTOCOL INFORMATION

2.1. Changes to the Protocol Defined Statistical Analysis Plan

Any changes from the planned statistical analysis specified in the protocol amendment 2 (Dated: 26/MAY/2016) are outlined below.

- Primary and supportive analyses:
 - Protocol specified “The MMRM model via PROC MIXED will include HbA1c change from baseline at post-baseline scheduled visits up to Week 26 as dependent variables; treatment, region, age category, weight category, background antidiabetic therapy, visit week and treatment-by-week interaction; baseline HbA1c as a continuous covariate; and subject as a random effect”.
 - Changes in the Reporting & Analysis Plan:
 - Week 1 visit is excluded from the MMRM due to small or zero change in HbA1c expected at Week 1 and the primary endpoint is change from baseline in HbA1c at Week 26. Inclusion of this visit in the MMRM model does not add much statistical efficiency, instead it likely leads to a non-positive definite estimated variance matrix and thus unstable estimate of treatment effect.
 - Baseline HbA1c-by-week interaction is added in the MMRM to allow for a more appropriate model fit by accounting for different coefficients of baseline at each post-baseline visit (Week 4, 8, 12, 16, 20 and 26) and thus avoid potential convergence issue due to insufficient model specification.

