7.1.1.1. Primary Analysis on Primary Efficacy Endpoint

The primary endpoint is the change from baseline in HbA_{1c} at Week 26. The primary analysis of the primary endpoint will be conducted using a mixed-effect model with repeated measures (MMRM) in the ITT Population. The primary analysis will include all HbA_{1c} values collected at scheduled visits from Week 4 up to Week 26. This will include values after hyperglycemia rescue and discontinuation from investigational product. Imputation under the non-inferiority null hypothesis for missing data will be incorporated [Koch, 2008]. Multiple imputation assuming missing at random (MAR) will be used to replace missing data of change from baseline of HbA_{1c} at Week 26 for all subjects in both treatment arms as a first step, and then to make all the imputed values for the liquid drug product arm worse by the non-inferiority margin 0.4.

Multiple imputation approach under MAR uses separate means and variance-covariance parameter estimation for each treatment arm (Carpenter and Kenward, 2013). Missing values for each subject will be imputed multiple times based on his or her own observed HbA_{1c} change from baseline values available and also based on the estimated means and variance-covariance from the treatment group where that subject is randomized to. This approach will be used for all missing data at Week 26 due to any reason including, but not limited to lost to follow-up and withdrawal consent. The details of implementing this multiple imputation approach are the following:

- **Step 1a:** Missing values at Week 26 will be imputed 100 times via SAS PROC MI (specifying BY treatment group, using MCMC statement with the option chain = multiple, including baseline and all post-baseline scheduled visits up to Week 26). As a result, 100 imputed datasets will be generated. Note: Only imputed values at Week 26 will be retained while the imputed values at other visits will be dropped from the imputed datasets.
- **Step 1b:** For each of the 100 imputed datasets from Step 1 the imputed values at Week 26 for the liquid drug product arm will be increased by 0.4.
- **Step 2:** Apply MMRM analysis as specified below for each of the 100 imputed dataset and save LSmeans (standard error) for each treatment arm at Week 26 and difference in LSmeans between treatment groups (standard error) from each of the 100 analyses.

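### The primary imputation model uses only HbA1c history within each arm, omits four baseline factors that the analysis model adjusts for, and SAP 2.1 does not record this narrowing

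*SAP*

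**What the plan says.** Protocol 9.4.1 describes the multiple imputation as arm-specific and says that "separate regression parameters are estimated on baseline covariates within each arm". It does not name those covariates, and it adds: "Further details of the imputation method for the primary analysis will be provided in the RAP".

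SAP 7.1.1.1 supplies the detail. It states: "Multiple imputation approach under MAR uses separate means and variance-covariance parameter estimation for each treatment arm". Each subject's missing values are "imputed multiple times based on his or her own observed HbA_{1c} change from baseline values available", together with the arm's means and covariances. The PROC MI step is run by arm, "using MCMC statement with the option chain = multiple, including baseline and all post-baseline scheduled visits up to Week 26". SAP 7.1.2 repeats this. The example code in SAP 11.11.1 has the same list: "VAR BASE CHG_W1 CHG_W4 CHG_W8 CHG_W12 CHG_W16 CHG_W20 CHG_W26".

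The model fitted to each imputed dataset is wider. Its code begins "MODEL CHG= BASE REGION WGTGR1 AGEGR1 PRIORDTX TRT01PN AVISITN", so region, weight group, age group and background therapy all enter, followed by the interactions.

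SAP 2.1 opens its list of departures with: "Any changes from the planned statistical analysis specified in the protocol amendment 2 (Dated: 26/MAY/2016) are outlined below". It gives two, both to the MMRM: Week 1 is dropped and a baseline-by-week term is added. The imputation covariates are not mentioned.

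**The concern.** Good practice is for an imputation model to contain at least the predictors in the analysis model. Here missing at random is assumed given arm and HbA1c history alone, whereas the MMRM conditions on four further factors. Three things follow.

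- **Main contrast.** A subject with little HbA1c history is imputed near the arm average for that baseline HbA1c, whatever the background therapy, age, weight or region. If those who leave differ from those who stay on such a factor, and the pattern differs by arm, the Week 26 contrast shifts.
- **Comparison with supportive analysis 1 (SAP 7.1.1.2).** That analysis fits the MMRM without imputation, so its missing-at-random assumption does condition on the four factors. The two analyses therefore differ in more than the intended 0.4 shift.
- **Subgroups (SAP 7.1.1.3).** Subgroup-by-treatment-by-visit terms for region, age, weight and background therapy are fitted to values imputed without those variables. This does not need arm-differential dropout to have an effect.

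**Working it through.** **Variable lists side by side**

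| | Imputation (SAP 7.1.1.1, 7.1.2, 11.11.1) | MMRM (same sections) |
|---|---|---|
| Baseline HbA1c | yes | yes |
| HbA1c changes | Weeks 1, 4, 8, 12, 16, 20, 26 | Weeks 4 to 26 (outcome) |
| Region, age group, weight group, background therapy | no | yes |

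Text and code agree, so this is not a coding slip.

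**The plan's own figures.** The documents give no figure on this point. The nearest is the sample size: margin 0.4, SD 1, true difference 0, one-sided 0.025. The noncentral t distribution gives power 0.9015 at 133 per arm and 0.8993 at 132, so 133 is reproduced. The missing fraction of 13% used below comes from the same section (Protocol 9.2.1; SAP 11.12.1).

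**One-arm bias.** Bias = missing fraction × factor effect left after HbA1c history × difference in factor mix between missing and observed subjects. The last two inputs are assumed.

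- Low: 0.13 × 0.1 × 0.1 = 0.001
- High: 0.13 × 0.3 × 0.3 = 0.012
- High, with opposite patterns in the two arms: 2 × 0.0117 = 0.023

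If the pattern and the effects are the same in both arms, the two errors largely cancel.

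**Simulation.** All settings other than the 13%, the 0.4 shift and the 150 per arm are assumed. Half of the missing subjects have baseline HbA1c only and half have one intermediate value. Imputation is by normal regression within arm (20 imputations), with 0.4 added in the liquid arm. A Week 26 ANCOVA stands in for the MMRM, and there are 1,500 runs. Strong effects include 0.4 for metformin, and moderate effects are half as large. In the opposite pattern the odds ratio of missingness for metformin is about 4.5 in one arm and its inverse in the other.

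| Scenario | True difference | Estimate, omitted / included | Non-inferiority concluded, omitted / included |
|---|---|---|---|
| Moderate effects, missingness unrelated | 0 | 0.052 / 0.052 | 84.9% / 84.0% |
| Strong, unrelated | 0 | 0.051 / 0.051 | 85.4% / 85.7% |
| Strong, opposite by arm | 0 | 0.032 / 0.055 | 88.4% / 83.9% |
| Strong, unrelated | 0.4 | 0.452 / 0.452 | 0.8% / 0.7% |
| Strong, opposite by arm | 0.4 | 0.437 / 0.460 | 1.0% / 0.9% |
| Strong, opposite, reversed | 0.4 | 0.483 / 0.461 | 0.2% / 0.6% |

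The simulation standard error of a rate near 85% is √(0.85 × 0.15 / 1500) = 0.9 points, so the first two rows show no difference. The extreme pattern moves the estimate by 0.022 to 0.024, in either direction. The planned shift itself contributes 0.13 × 0.4 = 0.052.

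**Subgroups.** Suppose 13% are missing in every subgroup and, as the worst case, these subjects have no post-baseline HbA1c. A subgroup's departure from the overall contrast is then carried only by the observed 87%, so it is shown at 1 − 0.13 = 0.87 of its size. Any HbA1c history brings this closer to 1.

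**The case against.** A reader might infer that the SAP contradicts the protocol. The documents do not support that. The protocol never lists the covariates, it leaves further detail to the SAP, and baseline HbA1c is a baseline covariate that stays in the imputation. Its next sentence, on arm-level means and covariances, is what the SAP implements. What remains is the plural, together with Protocol 9.4.5.2, which uses the same term for the set of covariates in the analysis. The regression has been reduced to one covariate and nothing in SAP 2.1 says so.

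A reader might also infer that the primary result is biased, or that non-inferiority could be falsely concluded. That does not follow either. Dropout that varies by factor is not enough: a residual factor effect and a pattern that differs by arm are also needed. Both documents expect similar missing-data patterns because the arms receive the same drug (Protocol 9.4.5.1; SAP 11.6.3.1). At a true difference of 0.4, false conclusions stayed at or below 1.0% in every simulated case, against 2.5% allowed.

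It is also fair to say that subjects who stop treatment are followed with HbA1c visits, so many will have history, and that the nine LMCF scenarios test larger departures. Supportive analysis 1 conditions on all four factors, but it also lacks the 0.4 shift, so it does not isolate this omission.

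Finally, region is an analysis covariate and not a randomization stratum (SAP 11.9.1). The omitted variables are better called factors than strata.

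**Conclusion.** The point stands as a minor one: an unrecorded narrowing of the imputation model and an improvement that costs almost nothing. The effect on the Week 26 contrast is about zero when missingness does not depend on the four factors differently by arm. It is 0.001 to 0.012 under the assumed one-arm inputs and about 0.02 in the extreme two-arm case, or roughly 6% of the 0.4 margin (0.023 / 0.4). In that extreme case, with a true difference of 0, the chance of concluding non-inferiority moved from 83.9% to 88.4%. This needs a missingness pattern that the documents give no reason to expect. No change to the non-inferiority decision is expected.

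The subgroup effect is more certain in direction but also limited: at 13% missing, a departure is shrunk by at most 13% under the worst case above. All sizes rest on assumed factor effects and dropout patterns. Only the 13%, the 0.4 and the sample size come from the documents.

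**What to change.** - In SAP 7.1.1.1, 7.1.2 and 11.11.1, add 0/1 indicators for age group, weight group, background therapy and three of the four regions to the PROC MI variable list, still run by arm. The list grows from 8 variables to 14. Running by arm lets each factor effect differ by treatment, which the subgroup contrasts need.
- In SAP 11.6.3.4, add the same indicators as predictors in Step 1 of the MNAR imputation, where no baseline factors are listed although the later ANCOVA uses the primary analysis covariates. State that the LMCF shift in Step 2 stays on the marginal HbA1c visit means. Otherwise the enlarged mean vector leaves the term last mean open to two readings.
- In SAP 2.1, log the imputation covariates. If the narrower model is kept, record and justify it there.

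The cost is a few lines of code and text. All variables are already collected, missing baseline covariates are expected to be none or minimal (SAP 11.6.3.2), and the sample size does not change. The change does not reach the sex, race, ethnicity and diabetes-duration subgroups, which are in neither model; their variables would have to be added separately if those displays matter.
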